### 7.5.3. Issues in Statistical Analyses

#### 7.5.3.1. Adjustments for Covariates

Not planned

#### 7.5.3.2. Handling of Dropouts or Missing Data

Described in “6.1 Handling of Missing Values” of this document.

#### 7.5.3.3. Interim Analyses and Data Monitoring

Not implemented

#### 7.5.3.4. Multicenter Studies

Analysis population(s): FAS

Analysis parameter: Titers and seroprotection rates for each type of antibody (anti-PRP, anti-diphtheria, anti-PT, anti-FHA, anti-tetanus, anti-poliovirus serotype 1, anti-poliovirus serotype 2, and anti-poliovirus serotype 3 antibodies)

Analysis method: For each site, for each group, for each antibody titer, and for each time point, the number of subjects, the number of subjects assessed for efficacy, the geometric mean, the geometric standard deviation, and the minimum, median, and maximum values will be calculated. In addition, the number of subjects, the number of subjects assessed for efficacy, the number of seroprotections, and the antibody seroprotection rates (%) will be calculated by site, group, antibody titer, and time point. The time profiles of the mean values of the antibody titers, by site, will also be presented.

#### 7.5.3.5. Multiple Comparison/Multiplicity

Multiplicity adjustment will not be performed, because the objective of this study is to verify the noninferiority of BK1310 to the control in terms of all of the anti-PRP antibody seroprotection rate and the antibody seroprotection rates for pertussis, diphtheria toxin, tetanus toxin, and attenuated poliovirus.

#### 7.5.3.6. Use of an “Efficacy Subset” of Patients

The analysis of the primary endpoint will be performed using the PPS.

#### 7.5.3.7. Active-Control Studies Intended to Show Equivalence

The objective of this study is to confirm the inferiority of BK1310 to a placebo in terms of the antibody seroprotection rates, and this study is therefore being conducted as a noninferiority confirmatory study with an active control. Detailed information about the analyses is presented in 7.5.1 and 7.5.2.

### 7.5.3.8. Analyses of Subgroups

#### 7.5.3.8.1. Seroprotection Rates for Each Type of Antibody, by Subgroup

Analysis population(s): FAS

Analysis parameter: The anti-PRP antibody seroprotection (titer  $\geq 1 \mu\text{g/mL}$ ) rate, and also the seroprotection rates for other antibodies (anti-diphtheria, anti-PT, anti-FHA, anti-tetanus, anti-poliovirus serotype 1, anti-poliovirus serotype 2, and anti-poliovirus serotype 3 antibodies) after the primary immunization or the booster immunization.

Analysis method: For the stratification factors shown in Table 7.5.3.8, for each group, the number of subjects, the number of subjects assessed for efficacy for each antibody, the number of seroprotections, the seroprotection rate (%), and the two-sided 95% confidence interval, will be calculated. Additionally, the 95% confidence intervals of the differences between the BK1310 group and the control group in the seroprotection rates will be calculated.

Table 7.5.3.8: Subgroups

Subgroup	
Sex	Male, Female
Age in months	$\geq 2$ and $< 3$ months, $\geq 3$ months
Antibody titer before the first dose in the population in question	For each antibody titer: $<$ reference value, $\geq$ reference value

#### 7.5.3.8.2. Time Profiles of Each Type of Antibody, by Subgroup

Analysis population(s): FAS

Analysis parameter: Titers of each type of antibody (anti-PRP, anti-diphtheria, anti-PT, anti-FHA, anti-tetanus, anti-poliovirus serotype 1, anti-poliovirus serotype 2, and anti-poliovirus serotype 3 antibodies)

Analysis method: For the subgroups shown in Table 7.5.3.8, for each group, for each analysis parameter, and for each time point, the number of subjects, the number of subjects assessed for efficacy, the geometric mean, the geometric standard deviation, the two-sided 95% confidence interval of the geometric mean, and the minimum, median, and maximum values will be calculated.

## 7.6. Safety Analyses

### 7.6.1. Adverse Events

The adverse event terms will be reclassified based on MedDRA/J Version 21.1.

#### 7.6.1.1. Incidences of Adverse Events And Adverse Drug Reactions

Analysis population(s): Safety analysis set

Analysis parameter: Adverse events (solicited adverse events, immediate reactions, other), adverse drug reactions (solicited adverse events, immediate reactions, other), serious adverse events, serious adverse

drug reactions, adverse events leading to discontinuation, adverse drug reactions leading to discontinuation

Analysis method: For each group, the number and proportion (and 95% confidence interval thereof) of subjects experiencing each type of event will be calculated.

#### 7.6.1.2. Individual Adverse Events

Analysis population(s): Safety analysis set

Analysis parameter: Adverse events, adverse drug reactions, serious adverse events and reactions, adverse events and reactions leading to discontinuation

Analysis method: For each group, the numbers and proportions of subjects experiencing each type of event will be calculated by event category (solicited adverse events, immediate reactions, other) and by MedDRA/J SOC and PT. Group totals will be shown, as well. Additionally, adverse events and adverse drug reactions will be tabulated by severity (mild, moderate, severe). If the same subject experiences the same event multiple times at different levels of severity, the event will be tabulated using the highest reported level of severity.

#### 7.6.1.3. Incidence of Solicited Adverse Events by Number of Doses

Analysis population(s): Safety analysis set

Analysis parameter: Adverse events and reactions that are considered solicited adverse events

Analysis method: For each number of doses, for each group, and for each MedDRA/J SOC and PT, the numbers and proportions of subjects experiencing each type of event will be tabulated by event category (solicited adverse events, immediate reactions).

#### 7.6.1.4. Adverse Events by Subgroup

##### 7.6.1.4.1. Solicited Adverse Events by Subgroup (Adverse Drug Reactions)

Analysis population(s): Safety analysis set

Analysis parameter: Adverse drug reactions classified as solicited adverse events

Analysis method: For the stratification factors shown in Table 7.6.1.4, for each group, the numbers and proportions of subjects experiencing each type of event will be calculated by MedDRA/J SOC and PT.

Table 7.6.1.4: Stratification factors

Stratification factors	
Sex	Male, Female
Age in months	$\geq 2$ and $< 3$ months, $\geq 3$ months

#### 7.6.1.4.2. Pyrexia (Solicited Adverse Drug Reaction)

Analysis population(s): Safety analysis set

Analysis parameter: Pyrexia (solicited adverse event) (adverse drug reaction)

Analysis method: For each number of doses, and both overall and by the presence or absence of simultaneous immunization with a pneumococcal vaccine, the number and proportion of subjects experiencing each type of event will be calculated (using the total number of administrated doses as the denominator).

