9.2.4 Safety Endpoints

9.2.4.1 Health Monitoring Diary

The (sub)investigator or a clinical research coordinator will have the legal guardian enter information for the following parameters in the health monitoring diary every day until Day 14 after vaccination with the investigational product. If the subject's pyrexia or symptoms do not return to normal by Day 14 after vaccination with the investigational product then, as a rule, the legal guardian will be instructed to enter information about them in the health monitoring diary until they return to normal. In addition, the (sub)investigator or a clinical research coordinator will transcribe (1) and (2) above into the case report form.

- (1) Body temperature (axillary)
- (2) The presence or absence of investigational product (investigational substance or control substance) vaccination site reactions (redness, swelling, induration, pain), and size (redness, swelling, induration) or severity thereof
- (3) The presence or absence of systemic reactions (irritability, crying, decreased appetite, decreased sleep, increased sleep), and the severity thereof

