9.2.4.2 Adverse Events

An adverse event is any clinically undesirable or unintended sign (including clinically significant test value abnormalities), symptom, or disease that occurs during the safety assessment period following vaccination with the investigational product, regardless of whether or not it is causally related to the investigational product.

Furthermore, vaccination site reactions (redness, swelling, induration, pain) and systemic reactions (pyrexia, irritability, crying, decreased appetite, decreased sleep, increased sleep), which are reactions that are specific to vaccination, that occur in the period up through Day 14 after vaccination with the investigational product will be considered pre-specified adverse events. Vaccination site reactions to other

vaccines that were administered at the same time will be considered normal adverse events, and will not be considered pre-specified adverse events. Axillary body temperature $\geq 37.5^{\circ}\text{C}$ will be handled as the adverse event "pyrexia." In addition, adverse events that occur within 30 minutes after vaccination with the investigational product will be considered immediate reactions.

(1) Symptoms or diseases

The (sub)investigator will confirm the presence or absence of adverse events based on the contents of the health monitoring diary that has been filled out by the legal guardian, as well as by questioning of the legal guardian and observation of the subject.

(2) Clinical laboratory test abnormalities

The (sub)investigator will handle as an adverse event any event that is judged to be a clinically significant abnormality.*

*: A "clinically significant test value abnormality" will be determined based on the following criteria.

- When there is a relationship to a clinical sign or symptom

However, if these symptoms or signs have been reported as separate adverse events, then there is no need to handle this test value abnormality as an adverse event.

- When a medical or surgical treatment has been administered for the test value abnormality in this clinical laboratory tests
- When the investigational product vaccination method has been changed (e.g., a change in the dose, treatment interruption, treatment discontinuation) because of the test value abnormality
- When the (sub)investigator determines for some other reason that the finding is a clinically significant abnormality

(3) Safety assessment period

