For events other than vaccination site reaction, which are pre-specified adverse events, the (sub)investigator will assess whether or not there is a "reasonable possibility" that the investigational product caused the adverse event in question. This assessment is made in consideration of the underlying disease, concomitant medical diseases, and other aspects of the natural course of the primary disease, concomitant therapies risk factors and factors other than the investigational product, and the temporal relationship between investigational product dosing and adverse event onset. For all vaccination site reactions (vaccination site redness, swelling, induration, and pain), which are pre-specified adverse events, the causal relationship to the investigational product will be classified as "there is a reasonable possibility." Adverse events for which it is thought "there is a reasonable possibility" of there being a causal relationship with the investigational product are considered adverse drug reactions.

1. Reasonable possibility

2. No reasonable possibility

5) Outcome

The outcomes of adverse events will be classified using the following 6 categories.

1. Recovered
2. Recovering
3. Did not recover
4. Recovered, but with sequelae
5. Death
6. Unknown

6) Day of outcome

The day of outcome will be classified according to the following criteria.

Recovered	: The day of resolution. However, if the day on which the subject recovered cannot be identified, then the day of outcome will be the day on which the outcome was confirmed or determined.
Recovering	: The day on which it was confirmed or determined that the subject was recovering.
Did not recover	: The day on which it was confirmed or determined that the subject had not recovered.
Recovered with sequelae	: The day on which it was confirmed or determined that sequelae were present.
Death	: The day of death. However, if the day of death cannot be determined, then this will be the day on which the death was confirmed or determined.
Unknown	: The day of death if the subject died due to a cause other than the adverse event in question and the outcome was unknown. Otherwise, this will be the day on which the outcome was confirmed or determined.

7) Follow-up

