### (2) The antibody titer measurement methods and antibody seroprotection rate criteria

Measurement Parameter		Measurement Method	Reference Value
Hib	Anti-PRP antibody concentrations	Enzyme-linked immunosorbent assay (ELISA)	$\geq 1 \mu\text{g/mL}$
			$\geq 0.15 \mu\text{g/mL}$
Diphtheria	Anti-diphtheria antibody concentrations	Neutralization method	$\geq 0.1 \text{ IU/mL}$
Pertussis	Anti-pertussis antibody concentrations	Enzyme-linked immunosorbent assay (ELISA)	$\geq 10.0 \text{ EU/mL}$
	Anti-FHA antibody concentrations		$\geq 10.0 \text{ EU/mL}$
Tetanus	Anti-tetanus antibody concentrations	Indirect agglutination (KPA)	$\geq 0.01 \text{ IU/mL}$

Polio	Anti-poliovirus antibody titers* (types 1, 2, and 3)	Neutralization method	$\geq$ 8-fold
-------	---	--------------------------	---------------

\*: Sabin strains

The proportions of subjects with the aforementioned reference antibody titers (the seroprotection rates) following immunization with the investigational product will be calculated.

Antibody seroprotection rate (%) =

$$[(\text{Number of subjects with antibodies}) / (\text{Number of subjects evaluated for efficacy})] \times 100$$

The number of subjects assessed for efficacy will be the number of subjects for whom antibody titer results have been obtained.

(3) Adverse drug reactions

Adverse events for which it is thought there is a reasonable possibility of there being a causal relationship with the investigational product are considered adverse drug reactions.

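### Fever by pneumococcal co-vaccination is tabulated only for fevers judged related to the study vaccine, which leaves the comparison open to differential attribution; all-cause rows should be added

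*SAP*

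**What the plan says.** The heading of SAP 7.6.1.4.2, "Pyrexia (Solicited Adverse Drug Reaction", and its analysis parameter, "Pyrexia (solicited adverse event) (adverse drug reaction", both restrict the table to fever classed as an adverse drug reaction. Results are given by dose number, overall and "by the presence or absence of simultaneous immunization with a pneumococcal vaccine".

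SAP 4.2 (3) and Protocol 9.2.4.2 define an adverse drug reaction by the causality judgement. Protocol 9.2.4.2 (4) attributes vaccination site reactions to the investigational product automatically. Other events are judged. The sentence that sets this rule begins "For events other than vaccination site reaction, which are pre-specified adverse events, the (sub)investigator will assess whether or not there is a", and the test it goes on to state is whether the product could reasonably have caused the event. Among the matters to be considered are "concomitant therapies risk factors and factors other than the investigational product". The temporal relationship to dosing is another.

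The raw measure needs no such judgement. Under Protocol 9.2.4.2 an axillary temperature of 37.5 °C or more "will be handled as the adverse event" pyrexia, and pyrexia through Day 14 is a pre-specified event. Body temperature is item (1) of the diary, and Protocol 9.2.4.1 says that site staff "will transcribe (1) and (2) above into the case report form". Protocol 8.5.1 permits a pneumococcal vaccine at the same visit, and Protocol 9.2.2 has its day, type and site recorded.

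**The concern.** A table that sets two strata side by side is easiest to read when the event means the same thing in both. Here an event counts only if the (sub)investigator links the fever to the study vaccine, and a pneumococcal vaccine given at the same visit is another candidate cause that the investigator may weigh. The stratifying factor can therefore enter the definition of the outcome. A fever rated related after the study vaccine alone might be rated unrelated after both vaccines, or the reverse if investigators lean the other way.

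The observer blind does not prevent this. Protocol 5.3.1.3 conceals which investigational product was given, whereas co-vaccination is recorded openly in the case report form.

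What is at stake is how the only planned co-vaccination safety table in an infant vaccine trial will be read. A difference between strata, or its absence, could reflect attribution rather than fever.

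**Working it through.** **Step 1: is attribution really a judgement for pyrexia?** Yes. Protocol 9.2.4.2 (4) exempts only redness, swelling, induration and pain at the vaccination site. Pyrexia is listed there as a systemic reaction, so it is judged case by case.

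**Step 2: can the co-administered vaccine enter that judgement?** It can. The causality text does not name co-administered vaccines, but its general wording on other therapies and other factors covers them. The pneumococcal vaccine is not an investigational product under Protocol 7.1.

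**Step 3: does another table show all-cause fever by co-vaccination?** No.

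| SAP section | Events | Split by |
|---|---|---|
| 7.6.1.1, 7.6.1.2 | Adverse events and reactions | Group; event category, SOC/PT and severity in 7.6.1.2 |
| 7.6.1.3 | Solicited events and reactions | Dose number, group |
| 7.6.1.4.1 | Solicited reactions only | Sex, age, group |
| 7.6.1.4.2 | Pyrexia, reactions only | Dose number, pneumococcal co-vaccination |
| 7.6.1.5 | Vaccination site reactions | Severity or dose number, group |

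**Step 4: how would unequal attribution act?** The plan states no figure to reproduce. The identities are:

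- rate shown = all-cause fever rate × probability that a fever is attributed to the investigational product
- ratio shown (with / without) = all-cause ratio × (attribution with / attribution without)

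Every input below is assumed, because the documents give neither fever rates nor attribution probabilities.

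| All-cause fever, without / with | Attribution, without / with | Shown, without / with | Difference shown (true), points | Ratio shown (true) |
|---|---|---|---|---|
| 40% / 40% | 0.9 / 0.9 | 36% / 36% | 0 (0) | 1.00 (1.00) |
| 40% / 40% | 0.9 / 0.7 | 36% / 28% | −8 (0) | 0.78 (1.00) |
| 40% / 40% | 0.9 / 0.5 | 36% / 20% | −16 (0) | 0.56 (1.00) |
| 40% / 40% | 0.7 / 0.9 | 28% / 36% | +8 (0) | 1.29 (1.00) |
| 20% / 40% | 0.9 / 0.9 | 18% / 36% | +18 (+20) | 2.00 (2.00) |
| 20% / 40% | 0.9 / 0.7 | 18% / 28% | +10 (+20) | 1.56 (2.00) |
| 20% / 40% | 0.9 / 0.45 | 18% / 18% | 0 (+20) | 1.00 (2.00) |

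For example, in the second row 0.40 × 0.9 = 0.36, 0.40 × 0.7 = 0.28, and 0.28 / 0.36 = 0.78. With equal all-cause fever of 20% or 60% and attribution of 0.9 and 0.7, the ratio stays at 0.78 and the difference becomes −4 or −12 points.

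The rows show three things. Equal attribution leaves the ratio intact. Unequal attribution can push it either way. In the last row it hides a true doubling. If fevers are counted whatever their causality, attribution drops out of the formula and the ratio shown is the all-cause ratio.

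**The case against.** **Attribution may hardly differ.** The test is a reasonable possibility, not sole or likeliest cause. A second vaccine on the same day does not remove that possibility, and the timing relative to the study dose is the same in both strata. This stands. A reader might infer that the comparison is distorted, but the documents support only that it is open to distortion.

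**The SAP states no aim for this table.** A reader might infer that it is meant to show whether co-vaccination raises fever. The SAP gives no hypothesis, test or interval there. The table can be read as describing reactions attributed to the study vaccine in each setting, and the sex and age table in 7.6.1.4.1 is restricted in the same way. This stands too, and is the reason to keep the planned rows rather than replace them.

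**All-cause fever has its own weaknesses.** It includes intercurrent illness. A reader might suppose that randomization balances this, but randomization balances the vaccine groups. Co-vaccination is only permitted and recorded, so the strata may differ in age, site or season. The adverse event record also involves judgement: under Protocol 9.2.4.2 (5) a diagnosis term is used as a rule, so a febrile illness might be recorded under its diagnosis. Working from diary temperatures avoids this second problem but not the first.

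**Little depends on it.** The table is descriptive, and SAP 7.6.1.3 already covers all solicited events by dose number and group. That limits the priority, but that table is not split by co-vaccination.

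**Conclusion.** The point holds in a limited form. The one table split by pneumococcal co-vaccination counts only attributed fever, the attribution may take the co-vaccination into account, and no planned table gives the all-cause counterpart.

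The size and direction of any distortion cannot be derived from the documents, and there is none in the ratio if investigators attribute fever equally in both strata. The ratios of 0.56 to 1.29 under equal true fever rates are consequences of assumed attribution probabilities between 0.5 and 0.9, not estimates for this trial.

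The overall safety comparison between vaccine groups does not rest on this table, and the primary noninferiority conclusion is unaffected. This is a low-priority improvement.

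**What to change.** In SAP 7.6.1.4.2, add rows for all solicited pyrexia: axillary temperature of 37.5 °C or higher through Day 14, any causality, derived from the diary temperatures transcribed to the case report form. Give them by dose number, vaccine group and pneumococcal co-vaccination status. The section does not currently name vaccine group as a split, so state it. Keep the adverse-drug-reaction rows alongside. Close agreement between the two sets would suggest that attribution matters little; a gap that differs between the strata would make its influence visible.

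Add a sentence saying that co-vaccination is not randomized and that the table is descriptive.

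The cost is a short SAP edit and a few extra rows, with no new data. The downside is that all-cause fever includes intercurrent illness. The change removes dependence on the causality judgement only; differences between the strata in age, site or season remain.

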9.2.2 Vaccination Status

The (sub)investigator or a clinical research coordinator will record the following information in the case report form.

- (1) Drug number
- (2) Day of vaccination with investigational product
- (3) Body temperature (axillary) prior to vaccination with the investigational product
- (4) Site of vaccination with the investigational product
- (5) Status of simultaneous immunization with a vaccine other than the investigational product (day of vaccination, type of vaccine simultaneously administered, site of vaccination)

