13.3.3 Safety

The numbers and proportions of subjects with adverse events and adverse drug reactions, as well as the confidence intervals, will be calculated by vaccination group.

In addition, the adverse event terms will be reclassified using MedDRA/J.

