## 6.4. Handling of Adverse Event Data When There Are Multiple Events In the Same Period

If the same PT occurs in the same subject occurs multiple times in the period in question (e.g., the safety assessment period or the specified period for each number of doses), then these will only be counted as a single event.

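### Does the pyrexia table by pneumococcal co-vaccination need a new denominator and an explicit split by vaccine group?

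*SAP*

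**What the plan says.** SAP 7.6.1.4.2 covers pyrexia as a solicited adverse drug reaction in the safety analysis set. Its rows are defined as follows: "For each number of doses, and both overall and by the presence or absence of simultaneous immunization with a pneumococcal vaccine". Its statistic is: "the number and proportion of subjects experiencing each type of event will be calculated (using the total number of administrated doses as the denominator".

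Four other places bear on how the table is read.

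- SAP 6.4 counts a repeated preferred term once within the period concerned, and gives as examples "the safety assessment period or the specified period for each number of doses". It does not assign either period to a particular table.
- Protocol 13.3.3 says that the numbers and proportions with adverse events and adverse drug reactions, "as well as the confidence intervals, will be calculated by vaccination group". SAP section 9 declares no departure from the protocol.
- The neighbouring tables name the group. SAP 7.6.1.3 begins "For each number of doses, for each group, and for each MedDRA/J SOC and PT", and SAP 7.6.1.4.1 says "for each group, the numbers and proportions of subjects experiencing each type of event will be calculated by MedDRA/J SOC and PT".
- Protocol 9.2.2 has the case report form record "Status of simultaneous immunization with a vaccine other than the investigational product", with the day and type of vaccine. Co-vaccination is therefore known for each vaccination, and one child can contribute doses both with and without pneumococcal vaccine.

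**The concern.** The numerator is worded as subjects and the denominator as doses. Among the adverse event tables in SAP 7.6.1.1 to 7.6.1.5.2, this is the only one with a dose denominator and the only one that does not name the group.

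If a row is pooled over a child's four doses and each child with any pyrexia is counted once, the quotient is neither the risk per dose nor the risk per child. It also falls as the number of doses per child in the row rises. Two pneumococcal strata with the same pyrexia risk could then show different figures, and that comparison is the purpose of the table. No other planned table gives pyrexia by pneumococcal co-vaccination, so the correct figure could not be read elsewhere. If the groups were merged as well, the table could not show whether fever with co-vaccination differs between BK1310 and control.

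**Working it through.** The plan states no figure for this table, so there is nothing to reproduce. The check is what each reading would print.

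**Inputs.** Up to 4 doses per child (protocol 8.4) and 130 children per group (protocol 6.1), so 130 × 4 = 520 vaccinations per group if all complete. The documents give no pyrexia rate. I assume a per-dose risk *p* of 20%, with a range of 10% to 40%, independent across doses. *k* is the number of doses per child in the row.

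**1. Rows for one dose number.** Here *k* = 1, so children dosed equal doses given. The per-child and per-dose proportions are both *p* = 20.0%. The denominator makes no difference.

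**2. Rows pooled over doses, counted once per dose period (SAP 6.4, second example).** The numerator is the number of doses followed by pyrexia: 520 × 0.20 = 104. The row shows 104/520 = 20.0%, whatever *k* is. This is a valid per-dose rate.

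**3. Rows pooled over doses, each child counted once over the whole period (SAP 6.4, first example).** The row shows [1 − (1 − *p*)^*k*]/*k*. At *p* = 20%:

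| *k* | Children ever febrile | Shown over doses |
|---|---|---|
| 1 | 20.0% | 20.0% |
| 2 | 36.0% | 18.0% |
| 3 | 48.8% | 16.3% |
| 4 | 59.0% | 14.8% |

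For *k* = 4 the figure shown runs from 8.6% (*p* = 10%) to 21.8% (*p* = 40%). If the same children are febrile after every dose, it drops to *p*/4, or 5.0% at *p* = 20%. If every child had three doses with pneumococcal vaccine and one without, equal risk would appear as 16.3% against 20.0%, a false gap of 3.7 points.

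**4. Which reading the text supports.** The row definition pairs *overall* with pneumococcal status after naming dose number. Read plainly, each dose number has three rows: all children, those with pneumococcal vaccine and those without. That is case 1. If *overall* instead pools doses, a table arranged by dose and divided by doses points to the dose period in SAP 6.4, which is case 2. Case 3 requires the analyst to pool the doses and also to choose the counting period that does not match the stated denominator.

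**5. What counts as a dose.** Control children receive two products at each vaccination, so counting injections would give 130 × 8 = 1,040 in place of 520. SAP 7.4 counts injections from 1 to 4 in both groups, so the unit is the vaccination occasion.

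**6. Would a per-child denominator be safer?** Not for rows pooled over doses. A child can sit in both strata with unequal numbers of doses. In the example in step 3, children with pyrexia over children vaccinated would show 48.8% against 20.0%, a false gap of 28.8 points. The dose denominator is the better choice for such rows.

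**7. Group.** Protocol 13.3.3 requires adverse drug reactions by vaccination group, SAP 7.1.5 fixes the two group displays, and SAP section 9 declares no change. Nothing in the SAP states an intention to merge the groups.

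**The case for a change.** The strongest case for a change is that two programmers could follow the SAP and print different numbers. SAP 6.4 permits both counting periods and SAP 7.6.1.4.2 chooses neither. For a single dose number a special denominator would be unnecessary, so mentioning the total of doses suggests that pooled rows were intended. The missing group phrase stands out because the six other adverse event tables have it. The repair would cost a few words and no new data.

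Most of these observations are right as text. The wording is loose, pooled rows are possible, and the counting period is not assigned to this table. What does not follow is a likely wrong result. The same dose denominator that hints at pooling also tells the analyst to count by dose, and that gives the correct rate. The group requirement stands in the protocol whether or not this subsection repeats it.

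**Conclusion.** The concern does not call for a change. It is a gap in wording that an analyst fills from SAP 6.4 and protocol 13.3.3. Rows for a single dose number are sound as written, and rows pooled over doses are sound when counted per dose period, the natural reading.

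The adverse figures (14.8% in place of 20.0%, or a false gap of 3.7 points between strata) rest on four assumptions together: pooled rows, once-per-child counting over the whole period, an assumed 20% risk independent across doses, and, for the gap, a three-to-one split of doses by co-vaccination. The documents support neither the risk nor the split.

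The table is descriptive and carries no test. Pyrexia by group, and by group and dose number, is available from SAP 7.6.1.2 and 7.6.1.3. The primary noninferiority analysis, its significance level and the sample size are unaffected.
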